Predictive Model. If we validate the proteins as diagnostic biomarkers, we will in this next part of the project ask whether this biomarker can be used to predict the future development of GVHD before its clinical signs become manifest. This statistical step will evaluate the value of the composite panel as a screening test for the risk of developing GVHD by computing the positive and negative predictive values. In order to be clinically useful, we expect that both values will be > 75%. In this case, we would expect that the biomarkers will correlate with subclinical disease. This possibility is likely, given that our preliminary data showed that TNFR1 levels in day 7 post- allogeneic transplant plasma

correlates with eventual severity and incidence of GVHD, and with overall survival^{33,34}. We propose to use our novel repository of samples and the clinical data from SA 1 to determine if any of these biomarkers have predictive ability when measured earlier in the patient's course. We are in a unique position to perform this analysis because our bank will contain samples that are collected from patients on a weekly basis during the first month after transplant. We will measure concentrations of the biomarkers at D7, D14, and D21 post- HCT (7 to 21 days prior to the onset of GVHD) and from similar time points in control patients, which will permit the generation of a kinetic curve for the individual biomarker.

We will develop a predictive model using Cox proportional hazard model with time dependent covariates. Time to GVHD development is a time to event outcome, protein biomarkers measured at D7, D14, and D21 post HCT are time dependent covariates, and treatment/control data and other clinical and demographic variables will be time independent covariates. To perform these analyses GVHD onset will be used as the event outcome. The control group includes the patients accrued on this protocol who do not develop GVHD. Two strategies will be used to model the time dependent biomarkers. One strategy is a simple linear interpolation and extrapolation of biomarker measurement to days other than day 7, 14, and 21. The second strategy is to model biomarker with either the linear trend or quadratic trend.

Although these two strategies will pose different Cox regression models with time

dependent covariates, they can be implemented into the likelihood model framework proposed by Wulfsohn and Tsiatis³⁵. We will follow this modeling strategy, and implement the model fitting in R. Given [name] extensive experiences in modeling longitudinal data with time dependent covariates^{36,37}, we are confident that we will be able to generate this time-dependent biomarker signature in predicting time to GVHD development.

12. APPENDIX D: GVHD scoring

Today's Clinical Acute GVHD Assessment					
Today's date Patient ID	Today's date Patient ID Karnofsky/Lansky				
Codes Differential diagnosis					
0 1 2 3 4	0 1 2 3 4 GVHD Drug Cond Infect TPN VOD Other				
		Rxn Reg			
Skin 🗆 🗆 🗆 🕬 I	oody rash:				
Liver 🗌 🗌 🗆 🗆 Curr	ent bili: [
GI 🗆 🗆 🗆 🗆 Vol:			Upper GI		
			Systemic		
agents: 🗌 CSA 🗌	Tacrolimus	🗆 Infliximab 🛛 🗆 Da	clizimab		
Pentost	atin 🛛 Sirolimu	s 🗌 Etanercept			
Prednisone Methylprednisolone Ontak Other					
Current steroid dose: Prednisone	mg/	kg/day; Methylprednisolone _	mg/kg/day		
Has the steroid dose been increased □ NO	d to ≥ 2.5 mg/kg/d	ay of prednisone (or 2 mg/kg	ı/day methylpred)? □YES		
If yes, date dose increased	; reason for dose i	ncrease: \Box GVHD flare \Box Oth	er (specify)		
Topical agents: Skin topical steroids	: 🗆 YES 🗆 NO;	Non-absorbed oral steroids (e.	g. Budesonide, Entocort) □ YES □ NO		
Chronic GVHD: Does the patient hav	e evidence of chro	nic GVHD? 🛛 YES 🗌 NO			
Codes Skin	Liver (bilirubin)	Lower GI (stool output/day)	Upper Gl		
0 No rash	≤ 2 mg/dl	Adult: < 500 ml/day Child: < 10 ml/kg/day	No protracted nausea and vomiting		
1 Maculopapular rash < 25% BSA	2.1-3 mg/dl	Adult: 500–1000 ml/day Child: 10 -19.9 ml/kg/day	Persistent severe nausea, vomiting with a positive upper GI biopsy		
2 Maculopapular rash 25 – 50% BSA	3.1-6 mg/dl	Adult: 1001-1500 ml/day Child: 20 – 30 ml/kg/day			
3 Generalized erythroderma (>50% BSA)	6.1-15 mg/dl	Adult: >1500 ml/day Child: > 30 ml/kg/day			
4 Generalized erythroderma (>50% BSA) plus bullous formation and desquamation > 5% BSA	>15 mg/dl	Severe abdominal pain with or without ileus, or grossly bloody stool or melena (regardless of stool volume)			
Signature		Date	e		

A sample Acute GVHD data record suggested for use in this trial is attached below.

A sample chronic GVHD data record suggested for use in this trial is attached below.

Today's Clinical Chronic GVHD Assessment

Today's date _____ Patient ID _____

	0	1	2	3
Skin	□ No changes	 < 18% BSA lichenoid, sclerodermatous, or ichthyotic involvement Eczema hypo or hyperpigmentation 	□ 18-50% BSA lichenoid, sclerodermatous, or ichthyotic involvement	 50% BSA involved Interference with ADLs due to impaired mobility Skin ulceration
Hair Loss	🗆 None	□ Mild (< 50%)	□ > 50%	
Joints	 No contractures Arthralgias Migratory arthritis 	 Persistent arthritis in 1 or 2 joints 	 Mild joint contractures (do not affect ADL) Polyarticular arthritis 	 Severe joints contractures (interfere with ADLs)
Oral	□ No changes	 Symptomatic but no change in diet 	 Able to eat most foods, although some dietary changes due to oral chronic GVHD 	 Unable to eat most foods due to oral chronic GVHD
Ocular	□ No changes	 Dry Eyes but not requiring therapy Keratoconjuctivitis, asymptomatic 	 Dryness of eyes requiring artificial tears, lachrymal plugging, or Schirmer's < 5 Keratoconjuctivitis, symptomatic 	 Pseudomembranes Corneal ulcerations Loss of vision
Esophagus	□ No changes	 Symptomatic but can eat regular diet 	 Dysphagia or odynophagia requiring dietary changes 	 Need for parenteral nutrition Web/stricture formation
Pulmonary	□ Asymptomatic	□ 75-90% FEV1/FVC □ Asthma	 Dyspnea with exertion 50-74% FEV1/FVC Desaturation with exercise 	 Dyspnea with normal activities <50% FEV1/FVC Requires supplemental oxygen
KPS/Lansky	 □ Asymptomatic and fully active (KPS 100%, ECOG 0) □ Lansky = 90-100% 	 Symptomatic and fully ambulatory; restricted in physical strenuous activity (KPS 80-90%, ECOG 1) Lansky = 70-80% 	 Symptomatic; ambulatory; capable of self-care, > 50% of waking hours are spent out of bed (KPS 60-70%, ECOG 2) Lansky = 50-60% 	 □ Symptomatic; limited self-care, spends > 50% of waking hours in bed, but not bedridden (KPS 40-50%, ECOG 3) □ Lansky = < 50%
GI manifestations	□ None	 □ Anorexia or malabsorption ± < 5% weight loss, or in children, growth deviation of < 5% of pre-transplant percentile after 1 year post-transplant 	□ Anorexia or malabsorption ± 5-10% weight loss, or in children, growth deviation of < 5% of pre- transplant percentile after 1 year post-transplant	 □ Anorexia or malabsorption ± > 20% weight loss, or in children, growth deviation of < 5% of pre- transplant percentile after 1 year post-transplant
Hematologic	 Thrombocytopenia not attributed to other causes > 100K 	 Thrombocytopenia not attributed to other causes > 75K 	 Thrombocytopenia not attributed to other causes > 50K 	□ Thrombocytopenia not attributed to other causes < 50K

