6. DATA AND SAFETY MONITORING PLAN

A meeting of the Data and Safety Monitoring Board was held on June 1, 2015. The Data Safety Monitoring Board consisted of DSMB Chair, [name], [name], [name], and [name]. The board reviewed and discussed the protocol. It was decided that since this is a low-risk, non-interventional study, it does not require a DSMB according to the NIH guidelines. Therefore, the DSMB has been eliminated.

Data and Safety will continue to be monitored by the study Principal Investigators.

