11. APPENDIX C: STATISTICS

Sample Size and Power Calculation. Three clinical endpoints are chosen as the primary hypotheses: D180 Post Therapy non-relapse mortality, D28 post-therapy non-response, and GVHD grade 1-4 onset. Seven biomarkers will be tested at either onset of GVHD or at day 14 post-HCT (median 14 days prior GVHD) in predicting these clinical endpoints. Therefore, the overall type-I error is justified by a fact of 7*3*2 = 42, and the per comparison type I error is controlled at 0.05/42 = 0.0012. The effect size is pre-specified by the expected sensitivity and specificity of a biomarker, which ranges from 0.60 to 0.70. The following table present the power of our study (N = 350) for three clinical endpoints. It shows that we shall have more than 91% power to test our hypotheses. Given the fact that our preliminary data show that one biomarker has a 85% sensitivity and specificity, our proposed sample size will have sufficient power to test our hypothesis.

Response Type and Rate	Sensitivity and Specificity		
	0.60	0.65	0.70
D180 Post Therapy non-relapse mortality (0.26)	0.91	>0.99	>0.99
D28 post-therapy non-response (0.41)	0.96	>0.99	>0.99
GVHD grade 1-4 onset (0.50)	0.98	>0.99	>0.99

Our 'pre-specified' expected sensitivity and specificity are based on our previous work (taking the median as cutoff) (see Table below, Vander Lugt et al. NEJM, 2013)

Sonsitivity and	l snacificity of	ST2 concentrations at	D14 to predict	six-month n	ost-HCT NRM
Sensitivity and	i specificity of	SIZ CONCENTRATIONS at	D 14 to predict	six-monui p	

0.1.1	Sensitivity	Specificity
Cutoff	(95% CI)	(95% CI)
75 th percentile	54% (50-59%)	83% (77-89%)
Median	75% (71-79%)	56% (48-64%)
25 th percentile	92% (89-94%)	29% (22-36%)

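### The Cox model for time to GVHD lists an undefined treatment/control covariate which, on the section's only definition of control, is fixed by the outcome

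*Protocol*

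**What the plan says.** The model is in Protocol Appendix C, under Predictive Model. It is meant to show whether markers at days 7, 14 and 21 after transplant foretell GVHD before it is clinically apparent.

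- Outcome: "Time to GVHD development is a time to event outcome".
- Event: "To perform these analyses GVHD onset will be used as the event outcome".
- Covariates: the markers are time-dependent, and "treatment/control data and other clinical and demographic variables will be time independent covariates".
- Comparator: "The control group includes the patients accrued on this protocol who do not develop GVHD". This comes two sentences after the covariate list. Just before the model is introduced, the section also says that markers will be measured "from similar time points in control patients".

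Section 6 (Data and Safety Monitoring Plan) drops the monitoring board "since this is a low-risk, non-interventional study", so there is no randomised or assigned arm. *Treatment/control* is not defined anywhere else.

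The SAP, dated February 2020, takes another route. It uses landmark analyses before transplant and at days 7, 14 and 21, with relapse as a competing risk. Its cause-specific hazards model adjusts for graft source, aGVHD prophylaxis, race/ethnicity and malignant disease. No treatment/control term appears.

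**The concern.** A covariate in a prediction model has to be known when the prediction is made. If *control* means a patient who does not develop GVHD, this covariate is known only once follow-up is over, and it carries the same information as the event indicator. Reading *treatment* as treatment for GVHD does not help, because that too follows from the event.

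What is at stake is the meaning of the marker coefficient. The question is which patients will develop GVHD. With the outcome on the right-hand side, the model answers only which of the patients who develop GVHD do so sooner. A marker that separates developers from non-developers well could then look useless. The marker hazard ratio printed beside the diverging group term may look unremarkable, so the error need not be obvious from that line of output.

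**Working it through.** **Inputs.** The documents give no effect size, power or sample size for this model, so there is no plan figure to reproduce. From the sample-size part of Appendix C: N = 350 ("The following table present the power of our study (N = 350) for three clinical endpoints"), a GVHD onset rate of 0.50, and marker sensitivity and specificity of 0.60 to 0.70. From section 1.1: onset typically two to eight weeks after transplant. Assumed here: follow-up to day 100, one fixed marker value per patient, no competing events, and two-sided 0.05 tests.

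**Step 1: the likelihood.** Let g = 1 for patients who develop GVHD and g = 0 for controls, with coefficient γ, and let x be the marker with coefficient β. Every event has g = 1. The partial-likelihood factor for case i is

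exp(βx_i + γ) / [Σ_cases exp(βx_j + γ) + Σ_controls exp(βx_k)]
= exp(βx_i) / [Σ_cases exp(βx_j) + e^(−γ) Σ_controls exp(βx_k)],

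with sums over those still at risk. For any β this rises as γ rises, so γ has no finite maximum. As γ grows, the control sum vanishes and what remains is the partial likelihood of the cases alone. The argument is unchanged if x is replaced by a time-dependent x(t).

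**Step 2: one simulated data set.** N = 350; marker mean 0.5 SD higher in cases; onset uniform over days 14 to 56.

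| γ fixed at | log-likelihood | marker HR |
|---|---|---|
| 0 | −952.72 | 1.385 |
| 1 | −855.09 | 1.247 |
| 2 | −791.55 | 1.120 |
| 4 | −736.61 | 0.973 |
| 8 | −721.95 | 0.920 |
| 15 | −721.59 | 0.919 |

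The likelihood climbs to a plateau while the marker effect disappears. In the simulations below, fixing γ = 15 matched the cases-only fit to within 5e-6 on the log-HR scale.

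**Step 3: size.** Two mechanisms bracket the range. In (a) the marker predicts whether GVHD occurs but not when (onset uniform over days 14 to 56). In (b) it acts by proportional hazards throughout, with a constant baseline hazard. Share retained = mean log-HR with the group term ÷ mean log-HR without it.

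Binary marker, 400 replicates per row:

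| Sens = spec | Mechanism | HR without → with term | Share retained | Rejection rate without → with |
|---|---|---|---|---|
| 0.60 | (a) | 1.76 → 1.00 | 0% | 0.95 → 0.06 |
| 0.65 | (a) | 2.35 → 1.01 | 1% | 1.00 → 0.06 |
| 0.70 | (a) | 3.21 → 1.00 | 0% | 1.00 → 0.06 |
| 0.60 | (b) | 1.79 → 1.11 | 18% | 0.97 → 0.09 |
| 0.65 | (b) | 2.43 → 1.18 | 18% | 1.00 → 0.20 |
| 0.70 | (b) | 3.36 → 1.24 | 18% | 1.00 → 0.25 |

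Continuous marker under (b), HR per SD, 300 replicates per row:

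| HR without → with term | Share retained | Rejection rate without → with |
|---|---|---|
| 1.36 → 1.06 | 20% | 0.98 → 0.11 |
| 1.66 → 1.12 | 23% | 1.00 → 0.26 |
| 2.04 → 1.21 | 26% | 1.00 → 0.57 |
| 2.72 → 1.40 | 34% | 1.00 → 0.91 |

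A continuous marker under (a) again keeps about 0%. Check by hand for the first binary row under (b): ln 1.11 / ln 1.79 = 0.104 / 0.582 = 0.18.

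A separate simulation with onset centred near day 28 and about 52% GVHD took an HR of 2.0 to 1.23 and 1.5 to 1.09. That is ln 1.23 / ln 2.0 = 0.30 and ln 1.09 / ln 1.5 = 0.21, inside the same range.

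**The case against.** The best defence is that the protocol never says that case/control status is a covariate. The phrase sits in a list with other clinical variables. Section 3.3 collects treatment variables fixed at transplant (conditioning, GVHD prophylaxis), and the Biomarker Panel part of Appendix C already adjusts for conditioning intensity. The comparator sentence could simply be naming the patients without an event. This stands to the extent that the outcome-defined covariate is a reading and not a stated rule. It is still the natural reading: *control* has no meaning as a conditioning or prophylaxis variable, and the section gives it only one definition.

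Two further points stand. The 2020 SAP lists its covariates and has no such term, so the fault lies in the 2015 text. The Cox model is also conditional on the markers first being validated for diagnosis. Appendix C addresses GVHD onset in addition by logistic regression and by predictive values, neither of which lists this covariate. A reader might infer that the study as a whole loses its ability to show prediction of GVHD; the documents do not support that.

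A reader might also infer that defining controls as patients who never develop GVHD biases the Cox fit in itself, because patients who die or relapse early are labelled by looking ahead. That does not follow. Developers plus non-developers are the whole enrolled cohort, and in a standard Cox fit a patient who dies early leaves the risk set at that time. Nothing in Appendix C credits such patients with extra time at risk. The label does harm only when it is entered as a covariate.

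**Conclusion.** The covariate sentence in Appendix C should be corrected. On its natural reading it puts the outcome among the predictors of time to GVHD, with a divergent group coefficient and a marker coefficient estimated from cases alone. That consequence is algebraic and does not depend on the simulations.

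The size does. Under the scenarios examined, about 66% to 100% of the marker log-HR is lost. The loss is total when the marker predicts occurrence but not timing. It is smallest for a strong continuous marker under proportional hazards, where the rejection rate was still 0.91. These figures rest on a fixed marker value and no competing events, whereas the plan has repeated, jointly modelled markers. They show the order of the loss and do not forecast a result.

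It would go too far to say that the plan certainly uses the outcome to predict itself, since the phrase is undefined, or that the SAP's analyses are affected, since the term is absent there.

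**What to change.** In the covariate sentence of Appendix C (Predictive Model), delete *treatment/control data*. If a real variable was meant, put its name there instead, provided that it is known at transplant: conditioning intensity or GVHD prophylaxis would qualify.

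Replace the control-group sentence with one along these lines: *All enrolled recipients form a single cohort at risk from transplant; those without GVHD remain at risk until death, relapse or last contact, and at each onset the comparison is with everyone still GVHD-free.* State as well whether death and relapse are treated as censoring or as competing events.

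This would bring Appendix C into line with the SAP's covariate list. The cost is two sentences, with no new data and no patients lost.

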1. BACKGROUND AND RATIONALE

1.1. Acute Graft-versus-Host Disease (GVHD)

Allogeneic hematopoietic cell transplantation (HCT) is a potential curative therapy for cancers of the blood and bone marrow, including leukemias that represent approximately one third of all cancer cases occurring among children and the leading cause of cancer deaths in children¹. Use of HCT has increased as new techniques have allowed for transplantation in patients who previously would not have been considered HCT candidates. Approximately 30,000 allogeneic HCTs will be performed worldwide in 2020; 20% of allogeneic HCT are performed in the pediatrics population. However, the efficacy of this procedure has been impeded by frequent and severe graft versus host disease (GVHD). The development of GVHD is tightly linked to the beneficial graft versus tumor (GVT) effect, the most potent form of immunotherapy. Nowadays, acute GVHD is measured by clinical symptoms in three organ systems: the skin, liver and gastrointestinal (GI) tract²⁻⁴. Acute GVHD typically occurs between two and eight weeks after transplant, but may occur later⁴, and is often clinically indistinguishable from other causes of clinical symptoms such as conditioning regimen toxicity, infection, or medication. Endoscopic biopsy is often used to confirm the diagnosis^{2,5}, but histologic severity on biopsy has not consistently correlated with clinical outcome^{3,5-7}. A noninvasive, reliable blood biomarker specific for GVHD with strong prognosis information would thus significantly aid in the management of patients with this disorder.

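### Linear interpolation of the day 7, 14 and 21 markers puts post-onset samples into the GVHD-onset Cox model and can make a non-predictive marker look predictive for onsets up to day 21

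*Protocol*

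**What the plan says.** The Predictive Model part of Protocol Appendix C asks whether the markers can foretell GVHD before clinical signs appear. The outcome is stated: "To perform these analyses GVHD onset will be used as the event outcome". The covariates are stated: "protein biomarkers measured at D7, D14, and D21 post HCT are time dependent covariates". Two ways of filling the other days are given. The first is "One strategy is a simple linear interpolation and extrapolation of biomarker measurement to days other than day 7, 14, and 21". The second is "The second strategy is to model biomarker with either the linear trend or quadratic trend". Of both, the appendix says "they can be implemented into the likelihood model framework proposed by Wulfsohn and Tsiatis", and that this modelling strategy will be followed.

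The same paragraph adds that "treatment/control data and other clinical and demographic variables will be time independent covariates", and then that "The control group includes the patients accrued on this protocol who do not develop GVHD".

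On timing, Section 1.1 states that "Acute GVHD typically occurs between two and eight weeks after transplant". Section 2.1 schedules sampling by calendar day, and a footnote to Table 3 in Section 4.2 lets samples up to day 28 move by 4 days either way. Appendix C describes the day 7, 14 and 21 samples as lying 7 to 21 days before onset.

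The SAP of February 2020 contains no interpolation. It describes landmark analyses before transplant and at days 7, 14 and 21, for both non-relapse mortality and acute GVHD, using the value at each landmark in patients who survived to it.

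**The concern.** In a Cox model with time-dependent covariates, the value attached to a risk-set day should be known by that day. A straight line between two draws breaks this rule, because every point on it depends on the later draw. When GVHD begins between the two draws, that later draw reflects established disease.

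Section 1.3 reports that the four panel proteins, elafin and REG3-alpha are higher in patients with GVHD than in those without. That comparison is between patients, not before and after onset in the same patient, but it makes a rise at onset plausible. The analysis could then report early prediction when it has only detected disease already present, which defeats its purpose.

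Extrapolation past day 21 is a separate weakness. It does not look ahead, but it stretches a line through two noisy values over most of the usual onset period.

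**Working it through.** The plan states no figure on this point, so there is none to reproduce. The check has four steps.

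**1. Which sample enters the risk set.** For day d between days 14 and 21, the interpolated value is (1 − w)·x14 + w·x21, with w = (d − 14)/7. For onset on day 17, w = 3/7, so the value is (4/7)·x14 + (3/7)·x21, and x21 is drawn 4 days after onset. The description of samples as 7 to 21 days before onset fits all three days only for onset on day 28 (28 − 21 = 7; 28 − 7 = 21). No rule removes samples drawn after onset.

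**2. How many onsets are exposed.** Appendix C places day 14 a median of 14 days before GVHD, so median onset is about day 28. Section 1.1 gives days 14 to 56 as typical. Assume lognormal onset with median 28 and 80% or 90% of onsets in that window (log-scale SD 0.541 or 0.421).
- Onset by day 21: Φ(ln(21/28)/0.541) = 0.30, or Φ(ln(21/28)/0.421) = 0.25.
- Onset between days 14 and 21: about 0.20 under either.

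With N = 350 and a GVHD rate of 0.50 (Appendix C power table), there are 175 cases: about 43 to 52 with onset by day 21, and about 34 between days 14 and 21.

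**3. Effect on a marker with no predictive value.** Simulation inputs are N = 350, 50% GVHD and the onset distributions above. The marker SD is 1.0 (0.8 between and 0.6 within patients; assumed). The marker is unrelated to GVHD before onset and raised by 0, 0.5 or 1 SD in samples on or after onset (assumed). The Cox model uses daily risk sets from day 8, with 300 to 400 runs per cell. Ranges cover the two onset distributions; hazard ratios are per 1 SD.

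| Follow-up and filling rule | No rise | 0.5 SD rise | 1 SD rise |
|---|---|---|---|
| To day 21, interpolated | HR 0.99–1.00; 3–4% | HR 1.40–1.42; 59–61% | HR 1.97–1.99; about 99% |
| To day 100, linear extrapolation after day 21 | HR 1.00; 4–5% | HR 1.01; 5–7% | HR 1.02–1.03; 13–14% |
| To day 100, held flat after day 21 | HR 0.99–1.00; 4–6% | HR 1.09–1.10; 19–21% | HR 1.18–1.20; 61–66% |
| Last prior value, either follow-up | HR 0.99–1.01; 5–6% | HR 1.00–1.02; 5–7% | HR 0.99–1.00; 4–7% |

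Percentages are rejections at 0.05. At the protocol's per-comparison level of 0.0012, the day-21 interpolated model still rejects in 14–20% of runs (0.5 SD) and 85–91% (1 SD).

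A second setting (N = 415 from the SAP, onset uniform on days 8 to 56, 200 runs) agrees. To day 21 it gives HR 1.37 and 1.86 with 65% and 99.5% rejection. With linear extrapolation to day 56 it gives HR 1.01 and 1.03 with 9% and 11%.

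**4. Why linear extrapolation dilutes the effect.** Extending the line through days 14 and 21 gives 2·x21 − x14 at day 28 and 6·x21 − 5·x14 at day 56. With independent errors, the error SD is multiplied by √(4 + 1) = 2.2 and √(36 + 25) = 7.8. Days 22 to 56 are 35 of the 42 days in weeks 2 to 8.

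Dropping post-onset samples alone is not enough. If interpolation is kept for patients still at risk (to day 21), rejection is 6–12% with no common time trend and 13–28% with a common trend of 0.3 per week up or down.

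**The case against.** The strongest reply has four parts.

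- **The large figures belong to a truncated analysis.** No document stops follow-up at day 21, and with linear extrapolation as worded the inflation is small. This stands. A reader might infer that interpolation inevitably creates false prediction, or that a hazard ratio near 2 is what the written plan would yield. Neither is supported: the effect needs a post-onset rise, reaches only onsets up to day 21, and is large only if follow-up is short or values are held flat afterwards. The small full-follow-up figure is no reassurance, however, since it arises from noise that would also bury a real signal.
- **The appendix commits to a joint likelihood.** It does, and such a model fitted only to pre-onset measurements would not look ahead. The appendix does not state that restriction, and a trend fitted through post-onset samples has the same fault.
- **The SAP uses landmarks.** A reader might infer that the SAP analysis inherits the bias. It does not inherit the interpolation. What remains is that the SAP does not say it replaces Appendix C and, for acute GVHD, requires only survival to the landmark rather than freedom from GVHD.
- **The model is conditional.** It is run only if the proteins are validated as diagnostic markers. Appendix C assigns the primary GVHD-onset endpoint to logistic regression, and time to GVHD is not a listed secondary objective. This limits the reach of the point.

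A reader might also infer that the outcome has been entered as a predictor, because controls are patients without GVHD and a treatment/control term is a covariate. The phrase is ambiguous and may mean treatment variables. It calls for a definition, not a finding of error.

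**Conclusion.** The concern holds in a limited form. The written rule lets a post-onset sample enter the risk set at onset for any case beginning between sampling days up to day 21, about 25% to 30% of cases under the assumed onset distributions. With assumed rises of 0.5 to 1 SD, a null marker then shows a hazard ratio of about 1.4 to 2.0 and about 60% to 99% false positives when follow-up ends at day 21. Over full follow-up the rate is about 5% to 14% with linear extrapolation and about 19% to 66% with a flat value after day 21. Using only prior values restores 4% to 7%. The onset distribution, marker SDs and rise sizes are assumptions; the documents give none of them beyond the median and the typical window. The fault lies in the protocol text, and nothing in the documents shows that a reported result used it.

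**What to change.** In Appendix C:
- Delete the interpolation and extrapolation strategy.
- State that each risk set uses only values measured before that day, by actual draw date, and that samples on or after GVHD onset are excluded.
- Name one method: the last prior value, a joint model fitted to pre-onset measurements, or the SAP landmark analysis.
- Define the treatment/control covariate, or remove it if it means GVHD status.

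In the SAP:
- State which method supersedes the Appendix C model.
- For the acute GVHD outcome, restrict each landmark to patients who are alive and GVHD-free.
- Confirm that no reported result used interpolated values.

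The cost is wording and, for the landmark restriction, a rerun of the acute GVHD analyses if it was not already applied. No new samples are needed; the joint model and the landmark analysis are already named in the documents, and the last prior value is simpler than either.
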